## Abbreviations

ABI – ankle-brachial index  
ATV – anterior tibial vein  
BMI – body mass index  
CFV – common femoral vein  
CHF – congestive heart failure  
CI – confidential interval  
CRF – case report form  
CRNM – clinically relevant non-major bleeding  
CTPA – computed tomography pulmonary angiogram  
CVD – chronic venous disease  
DIC – disseminated intravascular coagulation syndrome  
DUS – duplex ultrasound scan  
DVT – deep vein thrombosis  
ECS – elastic compression stockings  
FV – femoral vein  
GSV – great saphenous vein  
ICU – intensive care unit  
IPC – intermittent pneumatic compression  
IQR – interquartile range  
IRB – Institutional Reviewal Board  
ISTH – International Society of Thrombosis and Hemostasis  
ITT – intention-to-treat  
IVC – inferior vena cava  
LMWH – low-molecular-weight heparin  
NNH – number needed to harm  
NNT – number needed to treat  
PE – pulmonary embolism  
PeV – peroneal vein  
PTV – posterior tibial vein  
PV – popliteal vein  
SCD – sequential compression device  
SD – standard deviation  
SPECT/CT – single-photon emission computed tomography with a conventional computed tomography  
SSV – small saphenous vein  
SVT – superficial vein thrombosis  
UHF – unfractionated heparin  
VTE – venous thromboembolism

## 1. Background

Venous thromboembolism (VTE), including deep vein thrombosis (DVT), superficial vein thrombosis (SVT), and pulmonary embolism (PE), has been considered an important medical-social problem for decades. According to well-known epidemiological data, the VTE incidence in the general population is estimated as 1.0–1.9 cases per 1000 population per year, which can be further classified as 0.5–0.7 cases of pulmonary embolism and 0.5–1.2 cases of deep vein thrombosis. The official data of the Statistical Service of the Russian Federation exceed the average world figures and demonstrate the incidence of venous thrombosis at the level of 1.5–1.6 cases per 1000 population per year. It is well known that one of the important risk factors for VTE development is the recent inpatient treatment, especially accompanied by major surgery. Therefore, stratification of the hospitalized patients according to their individual VTE risk and providing adequate preventive measures are crucial during inpatient treatment. Early ambulation, elastic compression stockings, prophylactic anticoagulation, active blood drainage, and a combination of these methods significantly reduce the risk of postoperative VTE, especially fatal pulmonary embolism, in most surgical patients.

different IPC manufactures (with various pumps and sleeves) according to the clinical efficacy, compliance, patient's and nurse's satisfaction. The authors found some significant differences in the incidence of DVT, which ranged from 2.0% to 9.8% among the devices ( $p = 0.003$ ), and the best figures were observed for graduated sequential compression devices (SCD): 2.5% and 2.0% respectively. However, taking into account compliance and patient's and nurse's satisfaction, the best scores were demonstrated for the tight-length intermitted compression, which was associated with a DVT rate of 3.2%.

So, the second critical concern is compliance with IPC. Usually, compliance is far from 100% and typically ranges between 48 and 53%. It seems that compliance is higher in the intensive care unit (ICU) than in the profile surgical department. The main disadvantages of the IPC devices are related to their cumbersome size and their requirement to be connected to a static power source, both of which tended to confine patients to bed and delayed hospital discharge and rehabilitation. The studies that have aimed to assess compliance with IPC report that there might be a lack of device application as well as device functions. One study found that of all IPC devices that were applied, in 16% the pump did not function during the investigator's control visits.

The third point is that the minimal time of IPC application is unclear. Various studies have reported different durations of IPC application per day (14–20 h) depending on the type of device (portable or stationary). Another trial found that IPC in addition to pharmacoprophylaxis after orthopedic procedures was effective when applied for 6 h or more. However, the usual recommendation is to achieve 18 h of daily compliance.

These and other unresolved issues formed the basis of this study. The main hypothesis of the study was that the combination of IPC with standard preventive measures (above knee anti-embolic elastic compression stockings [ECS] and standard doses of low-molecular-weight heparin [LMWH]) would reduce the incidence of postoperative VTE in patients at extremely high risk (Caprini score of 11 or more). Also, to improve the compliance with IPC, we decided to find out if providing a 6-h free-of-compression night interval (from midnight to 6 am) with the preservation of 18 h of target duration for device application will result in better compliance combined with good clinical outcomes.

## 2. Rationale and objectives

**The rationale for the Study.** There are no randomized controlled trials examining the effect of the adjunct use of IPC with pharmacologic prophylaxis compared to pharmacologic prophylaxis (LMWH) alone in patients at extremely-high-risk (Caprini score of 11 and more) for VTE prevention.

**Use of Trial Results.** This trial expects to have significant patient safety implications. If the combined use of IPC with pharmacologic prophylaxis proves to be effective, this would change the standard of practice of thromboprophylaxis and will be a major advancement in patient safety.

**Study objectives:** To assess the superiority of IPC at the top of standard prophylaxis with LMWH and ECS compared to standard prophylaxis on postoperative asymptomatic venous thrombosis of lower limbs during inpatient treatment.

[figure not shown]
### **Secondary objectives:**

- To study the effect of IPC on the asymptomatic venous thrombosis occurrence during inpatient treatment in prespecified groups of patients:
  - Surgical profile,
  - Type of surgery,
  - The urgency of surgery,
  - The radicalism of surgery,
  - Type of anesthesia,
  - Malignant or benign disorder;
  - Preoperative, postoperative or delayed start of LMWH injections,
  - Pre-operative or post-operative IPC application,
- To study the effect of IPC on the isolated calf muscle DVT occurrence during inpatient treatment;
- To study the effect of IPC on the proximal DVT occurrence during inpatient treatment;
- To study the effect of IPC on the symptomatic PE occurrence during inpatient treatment;
- To study the effect of IPC on the fatal PE occurrence during inpatient treatment,

- To study the effect of IPC on the total VTE events that occur during inpatient treatment,
- To study the effect of IPC on the leg skin injury occurrence during inpatient treatment;
- To study the effect of IPC on the major and clinically relevant non-major bleeding occurrence during inpatient treatment;
- To study the compliance with IPC applied in the suggested regimen-required night free-of-compression interval;
- To study the effect of IPC on the symptomatic and asymptomatic venous thrombosis of lower limbs, symptomatic pulmonary embolism occurrence, and VTE related and VTE-non-related mortality during outpatient treatment and rehabilitation 30 and 180 days after surgery.

### 3. Design

A two-center, prospective, randomized (with independent allocation), open-label clinical trial with a blinded assessor for efficacy outcomes, enrolling patients at extremely high risk for postoperative VTE (Caprini score of 11 and more). The patients should be randomly allocated into two groups (experimental [IPC] group and control group) according to the VTE prophylaxis they received. Both groups will receive anti-embolic stockings and injections of LMWH, and patients in the IPC group additionally will receive IPC. The total duration of prophylaxis should amount of 1 month, and patients will be followed-up for 6 months with regular clinical examination and duplex ultrasound scans. Figure 1 represents the global design of the study.

[figure not shown]

**Figure 1.** The global design of the study.

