### **3.1. Randomization, Stratification, and Minimizing Bias**

The randomization should be performed independently for both clinical centers and should be based on the number of hospital medical records. After screening, only eligible patients will be randomized. If the last digit in the number of the hospital medical record is even, the patient should be allocated to the IPC group, and if odd, to the control group. If the last digit in the number of the hospital medical record is zero, the previous digit should be used. Both clinical centers contain multiple medical departments of different specialties, and the numbering of the medical records is performed sequentially through all departments. It starts at the beginning of the year (for example, the first medical record in 2017 is 1/17) and finishes at the end of the year. Taking into account the large admission rate to all medical departments, there is an extremely low probability that two consistently included patients would have sequential medical records. To reduce the bias of the deliberate non-inclusion of the patients with higher VTE risk in the IPC group all non-eligible subjects should be repeatedly evaluated for exclusion criteria by the Data Monitoring Committee.

After allocation to the group, the patient will be assigned an individual code, containing his index number, initials, and year of birth (for example, 1IV1961). This individual code will be used in all study documentation. The allocation list will be stored by the investigator. The blinded expert who will perform a duplex ultrasound scan (DUS) would not have access to the primary medical record or allocation list; he will use only individual patients code for identification. Also, to achieve blindness, most duplex scans will be performed in a separate room away from the patient's bed. If it will be impossible to transfer a patient to the room, the DUS will be performed at the bed, but the IPC device will be removed before the blinded expert's visit. A schematic diagram of the patient allocations is shown in Figure 2.

**Figure 1.** Scheme of the randomization and blindness.

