### **3.5. Endpoints and definitions**

**Primary endpoint:** asymptomatic venous thrombosis of the lower limbs detected by DUS during inpatient treatment.

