#### **Secondary endpoints:**

During inpatient treatment: isolated calf muscle DVT; proximal DVT; symptomatic PE; fatal PE; total VTE events; postoperative mortality; leg skin injury; combination of major and clinically, relevant non-major bleeding; and compliance with IPC.

At 30 days after surgery:

- Combination of symptomatic, asymptomatic venous thrombosis of the lower, limbs and symptomatic PE;
- VTE-related mortality;
- Non-VTE-related mortality.

At 180 days after surgery:

- Combination of symptomatic, asymptomatic venous thrombosis of the lower limbs, and symptomatic PE;
- VTE-related mortality;
- Non-VTE-related mortality.

Following DUS, distal DVT is defined as incompressibility of the affected calf vein, re-occlusion of the previously affected calf vein in case of personal DVT history. Proximal DVT is defined as incompressibility of the affected popliteal and thigh veins, re-occlusion of previously affected popliteal and thigh veins in case of personal DVT history, no blood flow with color flow imaging. Superficial vein thrombosis is defined as incompressibility of the affected superficial vein (GSV and its branches and SSV and its branches). Isolated calf muscle DVT is defined as occlusion of any calf veins except PTV, ATV, and PeV (sural veins, soleal veins). Proximal DVT is defined as occlusion of popliteal and all further cranial venous segments up to the iliac veins (PV, FV, CFV, external iliac vein, common iliac vein). Pulmonary embolism will be suspected according to the classical clinical symptoms and verified with SPECT/CT or CTPA by specific defects of contrast.

Major bleeding is defined by the ISTH criteria as: fatal bleeding; bleeding that is symptomatic and occurs in a critical area or organ; extra-surgical site bleeding causing a fall in hemoglobin level of  $\geq 20$  g/L, or leading to transfusion of  $\geq 2$  units of whole blood or RDC, with temporal association within 24–48 h to the bleeding; surgical site bleeding that requires a second intervention; or surgical site bleeding that is unexpected and prolonged or sufficiently large to cause hemodynamic instability, as assessed by the surgeon.

Clinically relevant non-major (CRNM) is defined as any other bleeding, that does not match the criteria of major but needs some specific measures for hemostasis and/or interruption or preliminary abortion of anticoagulation.

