#### **5.4. Examination during inpatient treatment**

The following data on surgical procedure should be obtained from the medical records after intervention: the surgical profile (e.g., abdominal, thoracic, neck, pelvis, cranial), type of surgery (open, endoscopic, endoscopy assisted), urgency of surgery (emergent = performed in 0–2 h after admission, urgent = performed in 0–6 days after admission, elective = performed independently at the time of admission), radicalism of surgery (radical, palliative), type of anesthesia (general, regional, combined), surgery duration, blood loss, and intraoperative infusion.

The routine clinical examination of the patient will be performed in a daily manner with special attention to the possible complications, such as DVT, SVT, PE, bleeding, and leg skin injury. IPC sleeves should be removed for 15–20 mins every day for skin inspection and investigation of pedal pulsation. Consultation of any relevant specialist

(cardiologist, neurologist, pulmonologist, infections) should be performed if any complication or development of new co-morbidity will be observed during the follow-up.

DUS should be performed every 3–5 days after surgery and in emergency manner if any clinical suspicion for DVT or SVT appeared. In an emergency manner, DUS may be performed by a blinded expert or specialist on duty on weekend and holidays. However, all conclusions of non-investigational medical staff must be verified by a blinded expert.

SPECT/CT or CTPA should be used to verify PE in an emergency manner if clinical suspicion appeared. An autopsy must be performed in all died patients to verify the absence of DVT and PE.

In case of any clinical suspicion for a VTE event, IPC should be interrupted until final verification of the diagnosis. In the case of positive DUS, CTPA, and SPECT/CT, the therapeutic anticoagulation should be prescribed, and IPC should be removed. In the case of clinical suspicion for VTE with negative results of instrumental tests, IPC should not be returned until the proper diagnosis that mimics VTE will be found.

Any revealed leg skin lesion should be judged individually for the possibility to continue ECS and IPC application. If the decision will be made to stop IPC, the patient should be withdrawn from the study according to the protocol.

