### **5.5. Examination during outpatient treatment**

After discharge, patients should be evaluated at 30 and 180 days after surgery. The target content of examination should include DUS and clinical examination. However, it is allowed to make a phone call to interview the patient about his status and any new symptomatic VTE events.

During the clinical examination, the investigator should revise the patient's medical records for any symptomatic or asymptomatic VTE episodes, confirmed by appropriate radiological tests.

DUS in the outpatient settings should be performed by a blinded expert using the same methodology. Any new postthrombotic change (residual venous obstruction, valvular insufficiency) revealed on the 30th or 180th day of observation and had not been documented previously should be considered as a new venous thrombosis corresponding with the secondary endpoint.

If the patient would not be available for head-to-head examination, the phone call should be made, and the subject should be interviewed with special attention to possible

clinical signs of symptomatic VTE episode. If the patient will report a VTE episode confirmed by an appropriate test, he should be asked to send the medical records on this issue by e-mail. If the investigator would find that a patient had died, he should to gather appropriate documentation, confirming the cause of the lethal outcome.

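### The design claims a blinded assessor for efficacy outcomes, but blinding is described only for duplex scans; PE, cause of death and post-discharge records have no described blinded step

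*Combined protocol and SAP*

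**What the plan says.** **The claim.** Section 3 (Design) calls the study an "open-label clinical trial with a blinded assessor for efficacy outcomes".

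**The blinding procedure.** Section 3.1 describes it for one role: "The blinded expert who will perform a duplex ultrasound scan (DUS) would not have access to the primary medical record or allocation list". That expert works from the patient code, and scans take place away from the bed or after the device is removed. On the other side, "The allocation list will be stored by the investigator". Section 3.1 also sets allocation by the last digit of the hospital record number: even goes to IPC and odd to control, and a final zero passes the decision to the preceding digit.

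**The endpoints.** The primary endpoint (Section 3.5) is "asymptomatic venous thrombosis of the lower limbs detected by DUS during inpatient treatment". The inpatient secondary endpoints begin with "isolated calf muscle DVT; proximal DVT; symptomatic PE; fatal PE; total VTE events; postoperative mortality". At days 30 and 180 they are a composite of symptomatic or asymptomatic leg thrombosis and symptomatic PE, together with VTE-related and non-VTE-related mortality.

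**How the non-duplex outcomes are established.** Section 3.5: "Pulmonary embolism will be suspected according to the classical clinical symptoms and verified with SPECT/CT or CTPA". Section 5.4 requires an autopsy for every inpatient death. Section 5.5 has the investigator look through medical records for VTE episodes confirmed by radiological tests, allows a telephone interview in place of a visit, and has patients who report an episode e-mail their records. On death it says: "If the investigator would find that a patient had died, he should to gather appropriate documentation, confirming the cause of the lethal outcome".

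**The concern.** In an open-label trial, blinded outcome assessment is the main protection against bias in deciding what counts as an event. Section 3 promises that protection for efficacy outcomes in general, and a reader will take it to cover PE and VTE-related death. The procedures reach only the ultrasound room.

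The uncovered outcomes involve judgement. Section 3.5 gives no definition of a VTE-related death, so someone must decide which deaths qualify. Someone must also decide whether an e-mailed outside report is a confirmed new episode. If that person knows the arm, the call can drift with expectation. Section 2 expects a positive result to change practice, and PE and VTE death are outcomes that readers will weigh when they consider that.

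**Working it through.** The claim carries no figure of its own, so the main check sets the sections side by side. A short calculation then shows what one classification could do.

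**Step 1. Outcome by outcome.**

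| Outcome | How it is established | Blinded step in the available text |
|---|---|---|
| Asymptomatic inpatient thrombosis (primary) | Trial DUS (3.5, 5.3) | Yes (3.1, 5.3) |
| Calf muscle and proximal DVT on inpatient DUS | Trial or on-duty DUS (5.4) | Yes; on-duty scans need a blinded check (5.4) |
| Symptomatic PE, inpatient | SPECT/CT or CTPA on clinical suspicion (3.5, 5.4) | None stated; no reader named |
| Fatal PE, inpatient | Autopsy (5.4) | None stated; no assessor named |
| Total VTE events, inpatient | Sum of the above | DUS part only |
| Day-30 and day-180 composite, trial scan done | Outpatient DUS (5.5) | Yes for the scan |
| Day-30 and day-180 composite, from records or telephone | Investigator's record review and interview; e-mailed records (5.5) | None described |
| VTE-related vs non-VTE-related death, days 30 and 180 | Documents gathered by the investigator (5.5) | None described; classifier not named |
| Postoperative mortality, inpatient | Fact of death | Needs no judgement of cause |

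The Data Monitoring Committee does not fill the gap. Its one stated task, in Section 3.1, is to re-check exclusion criteria in non-eligible subjects.

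**Step 2. Can the arm be known?** After discharge, yes in principle: Section 5.5 gives the records to the investigator, and Section 3.1 gives the investigator the list. For inpatient PE and autopsy no reader is named, but the list is not needed. A report that bears the trial hospital's record number shows the arm through its last digit. Silence about blinding therefore means unblinded by default unless the number is removed.

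**Step 3. What one classification can do (assumed counts).** The documents give no PE or VTE-death rate for this population, so the counts below are assumptions. Section 8 arrives at 200 subjects and doubles that: 2 × 200 = 400, or 200 per arm. Secondary endpoints use the two-tailed Fisher exact test.

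| Events, control vs IPC (200 per arm) | Two-sided p |
|---|---|
| 10 vs 1 | 0.011 |
| 9 vs 1 | 0.020 |
| 8 vs 1 | 0.037 |
| 7 vs 1 | 0.068 |
| 6 vs 1 | 0.122 |
| 5 vs 1 | 0.22 |

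One reclassified control case crosses 0.05 between 8 vs 1 and 7 vs 1. It does not cross between 10 vs 1 and 9 vs 1, and 5 vs 1 is far from 0.05 before any change. With the planned 10% withdrawal, 0.9 × 200 = 180 per arm, and 8, 7 and 6 vs 1 give 0.037, 0.067 and 0.121.

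**The case against.** The strongest reply is that the trial's conclusion does not rest on these endpoints. The main objective in Section 2 and the primary endpoint both concern asymptomatic thrombosis on DUS, which is blinded, and on-duty emergency scans are checked by a blinded expert. Section 8 makes no multiplicity adjustment and itself warns that inferences may not be reproducible, so a secondary p-value on one side of 0.05 settles little. PE needs imaging, inpatient deaths need autopsy, and outside episodes need a confirming test, all of which limit the room for opinion. This stands, and it confines the point to secondary endpoints.

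A reader might go further than the documents allow in three ways.

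- **That an unblinded investigator judges every PE and every death.** For inpatient PE and autopsy no judge is named; the defect there is silence. For deaths after discharge the text says that the investigator gathers documents. That he also classifies the death is a fair inference, but it is not stated. That the list-keeper and the record reviewer are one individual is likewise implied only.
- **That the trial drops its own safeguard after discharge.** The rule that "all conclusions of non-investigational medical staff must be verified by a blinded expert" appears in the paragraph on emergency DUS done in hospital by the specialist on duty. It was never a rule about outside records.
- **That the split into VTE-related and other death also applies in hospital.** It is an endpoint only at days 30 and 180. The inpatient endpoints are fatal PE and overall postoperative mortality.

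Absence must also be worded with care. The design and blinding figures are not shown, and part of the document between Section 8 and the references was not available; a further assessor role could be named there.

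**Conclusion.** The point holds for secondary endpoints. The blinding claimed in Section 3 is wider than any procedure in the available text, which blinds duplex assessment only. It is clearest after discharge, where the investigator both handles the outcome records and, under Section 3.1, stores the allocation list. For inpatient PE and fatal PE, the plan does not say who reads the evidence or whether that person is blinded, and the allocation rule makes an unredacted hospital report revealing.

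The affected endpoints are symptomatic PE, fatal PE, total VTE, the day-30 and day-180 composites, and VTE-related mortality with its non-VTE counterpart. The blinded primary endpoint is untouched, and nothing here suggests that its result would be biased through outcome assessment.

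No magnitude can be derived from the documents. A reader might infer from the 8 vs 1 example that one call would decide these endpoints. That holds only if the counts happen to fall near the 0.05 boundary.

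The verdict assumes that the sections not available name no further blinded assessor, and that PE and autopsy reports carry the hospital record number unless it is removed.

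**What to change.** 1. **Outside venous-thrombosis records.** Have the existing blinded duplex experts confirm these from copies labelled with the patient code, with the hospital record number and any mention of IPC removed. State that their call is the one analysed.
2. **PE and cause of death.** Choose one of two options and write it down:
   - classify from imaging and autopsy reports that are coded and redacted in the same way, by a named role without access to the allocation; or
   - narrow the Section 3 statement to a blinded assessor for duplex ultrasound outcomes, and report the PE and cause-of-death endpoints as open-label.

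The documents do not show that the duplex experts are qualified to read CTPA, SPECT/CT or autopsy findings, so the first option should not simply be assigned to them.

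**Cost.** Step 1 and the first option need protocol wording, some redaction work and time from a reader; patients undergo nothing extra. The number of reports cannot be estimated from the documents. The second option costs little more than a changed sentence and labels in the report, at the price of a narrower blinding claim.
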